5.3 Lifestyle Considerations

No restrictions required.

5.4 Screen Failures

A screen failure occurs when a participant who has consented to participate in the clinical study but is not subsequently assigned to study intervention (vericiguat). A minimal set of screen failure information is required to ensure transparent reporting of screen failure participants to meet the CONSORT publishing requirements and to respond to queries from regulatory authorities. Minimal information includes demography, screen failure details, last visit date and SAE.

Individuals who do not meet the criteria for participation in this study (screen failure) may be rescreened once. The following conditions are pre-requisites of re-screening:

- A minimum of 1 month between the initial Screening visit and re-screening.
- Before re-screening, new documented informed consent must be obtained.
- Allocation of a new participant identification number.
- All screening assessments for the study must be repeated.

29 NOV 2023 Page: 20 of 44

5.5 Criteria for Temporarily Delaying Study Intervention

Not applicable.

6. Study Intervention and Concomitant Therapy

Study interventions are all pre-specified, investigational and non-investigational medicinal products, medical devices and other interventions (e.g., surgical and behavioral) intended to be administered to the study participants during the study conduct.

Refer to the approved labeling / most recent investigator's brochure for vericiguat for more details regarding study intervention properties and formulation.

6.1 Study Intervention Administered

Study intervention should be taken orally with food at the same time each day, preferably in the morning. If a dose is missed, it should be taken as soon as the participant remembers on the same day of the missed dose. But there should be consistency with respect to dosing intervals (the recommendation is to have at least a 20-hour interval between doses). Participants should not take 2 doses of study intervention on the same day. The investigator should be informed if the dose of Vericiguat taken has exceeded the scheduled dose.

Intervention Label	Vericiguat
Intervention Name	Vericiguat
Intervention Description	Tablet 5 mg/day
Type	Small molecule drug
Dose Formulation	Tablet
Unit Dose Strength(s)	5 mg
Dosage Level(s)	1 x 5 mg daily for 14 (+4) days
Route of Administration	Oral
Use	Experimental
Sourcing	Vericiguat will be provided centrally by the Sponsor.
Packaging and Labeling	Vericiguat tablets are available in high density polyethylene (HDPE) bottles with a white child resistant closure and induction seal. The packaging configuration is 18 tablets Vericiguat 5 mg per bottle. The bottles will be labelled as required per country requirement.
Current/Former Name(s) or Alias(es)	VERQUVO®, BAY 1021189

Table 6-1: Study Intervention Administered

6.2 Preparation, Handling, Storage, and Accountability

- 1. Only participants enrolled in the study may receive study intervention and only authorized site staff may supply, prepare or administer study intervention.
- 2. All study intervention must be stored in a secure, environmentally controlled, and monitored (manual or automated) area in accordance with the labeled storage conditions with access limited to the investigator and authorized site staff.

29 NOV 2023 Page: 21 of 44

3. The investigator is responsible for study intervention accountability, reconciliation, and record maintenance (i.e., receipt, reconciliation, and final disposition records). Study intervention returns, reconciliation and destruction return information will be captured in IRT.

4. Further guidance and information for the final disposition of unused study interventions are provided in the site file.

Handling/Storage/Accountability at the participant's home

Participants will follow the instructions provided by authorized site staff for storage and administration of study intervention at home, as well as for return of unused study intervention to the site.

6.3 Assignment to Study Intervention

Randomization is not applicable for the study. All participants will receive the same study intervention.

All participants will be centrally assigned to the study intervention using an IRT. Enrollment caps defined in Section 5 will be managed by the IRT. Participants will be given a unique PID (9 digit number) at the start of screening. The PID consists of a unique country number (digits 1 to 2), unique center number (digits 3 to 5) and the participant number within the center (digits 6 to 9). Participants who meet the entry criteria will be sequentially assigned to a treatment allocation number (TNR) in ascending order.

6.4 Blinding

Not applicable. This is an open label study. For details on ensuring data integrity, see Section 9.4.

6.5 Study Intervention Compliance

A participant will receive exactly one bottle of vericiguat 5 mg tablets containing 18 tablets for any unforeseen events (e.g. loss or damage of single tablets or to allow for visit window).

Compliance with study intervention (vericiguat) self-administered at home between Visit 1 and Visit 2, will be assessed at Visit 2 (Day 14). Compliance will be assessed by counting returned tablets during the site visit and documented in the source documents and relevant form.

Deviation(s) from the prescribed dosage regimen should be recorded. Any discrepancies between actual and expected amount of returned study intervention must be discussed with the participant at the time of the visit, and any explanation must be documented in the source records. An adequate record of receipt, distribution, and return/destruction of all study intervention must be kept.

A record of the quantity of vericiguat tablets dispensed to and administered by each participant must be maintained and reconciled with study intervention and compliance records. An adequate record of receipt, distribution, and return/destruction of all study intervention must be captured on the dispensing log and/or in the IRT. Intervention start and stop dates, including dates for intervention delays will also be recorded in the CRF/eCRF.

Participants will be instructed to take study intervention as scheduled, and to return all of the study intervention packaging including unused study intervention and empty packaging.

29 NOV 2023 Page: 22 of 44

Study intervention tablets not returned will be considered to have been taken unless otherwise specified. At the end of the study, any remaining study intervention will be collected and destroyed as per local regulations. Any discrepancies between the returned and expected returned study intervention should be explained.

6.6 Dose Modification

The intention of the protocol is to maintain participants on the 5 mg dose of study intervention for the 2-week treatment period. Dose modifications are not planned within the scheme of this study. See Section 7.1.1 for details on temporary discontinuation of study intervention.

6.6.1 Retreatment Criteria

All participants entered into the study will be treated from Day 1 to Day 14 inclusive. See Section 7.1.2 for details on treatment resumption after temporary interruption of study intervention

6.7 Continued Access to Study Intervention after the End of the Study

No continued access to the study intervention is planned following the end of the study. Participants may continue treatment on commercially available vericiguat at the discretion of their treating physician.

6.8 Treatment of Overdose

In this study, an overdose is any dose higher than 5 mg vericiguat QD.

Limited data are available with regard to overdosage in patients treated with vericiguat. In the event of an overdose, hypotension may result. Symptomatic treatment should be provided. Vericiguat is unlikely to be removed by hemodialysis because of high protein binding.

In the event of an overdose, the investigator should:

- Evaluate the participant to determine, in consultation with the medical monitor, if possible, whether study intervention should be interrupted or whether the dose should be reduced.
- Closely monitor the participant for any AE/SAE and laboratory abnormalities
- Document the quantity of the excess dose as well as the duration of the overdose.

Decisions regarding dose interruptions or modifications following a suspected overdose will be made by the investigator in consultation with the medical monitor based on the clinical evaluation of the participant.

6.9 Prior and Concomitant Therapy

Any medication or vaccine (including over-the-counter or prescription medicines, recreational drugs, vitamins, and/or herbal supplements) that the participant is receiving at the time of enrollment or receives during the study must be recorded along with:

- Reason for use
- Dates of administration including start and end dates

29 NOV 2023 Page: 23 of 44

Dosage information including dose and frequency

All participants should receive GDMT based on locally relevant guidelines such as ESC and ACC/AHA Guidelines for Management of Heart Failure applied individually to the discretion of the treating investigator and in line with individual tolerability, aiming at reflecting the current standard of care in the largest proportion of patients (Heidenreich et al. 2022, McDonagh et al. 2021). This includes medications such as beta blockers, ACEIs, ARBs, ARNI, MRAs, hydralazine-nitrate combinations, SGLT2 inhibitors, ivabradine, and cardiac device therapies such as ICDs and biventricular pacemakers. At least 30% of participants receiving an ARNI and 30% a SGLT2i should be enrolled in the study in order for the study to meet contemporary GDMT standards. Dose changes in GDMT medications (RAS blockade, Beta-blocker, MRA, or SGLT2i) or oral diuretics should be discouraged, except when mandated by known side-effects for individual drug classes (e.g., hyperkalemia for MRA or angioedema for ACE-inhibitors / ARNI). Use of short and long-acting nitrates is permitted.

Medications specifically prohibited in the exclusion criteria are not allowed for concomitant use with study intervention. In particular, the following are prohibited:

- Use of IV diuretic or inotropes
- PDE5i such as vardenafil, tadalafil, and sildenafil
- sGC stimulators (e.g., riociguat or vericiguat)

If there is a clinical indication for any medications specifically prohibited, discontinuation from study intervention may be required. This would result in not meeting criteria for the primary endpoint treatment tolerability. The investigator should discuss any questions regarding this with the medical monitor. The final decision on any medical therapy rests with the investigator and/or the participant's primary physician. However, the decision to continue the participant on study intervention requires the mutual agreement of the investigator and the participant and the information of the Sponsor.

The medical monitor should be contacted if there are any questions regarding concomitant or prior therapy.

6.9.1 Rescue Medicine

No rescue or supportive medications are specified for use in this study.

7. Discontinuation of Study Intervention and Participant Discontinuation/Withdrawal

Discontinuation of specific sites or of the study as a whole are detailed in Section 10.1.

7.1 Discontinuation of Study Intervention

Discontinuation is defined as the inability to complete treatment between Visit 1 and Visit 2. One missing/forgotten dose is permitted. All cases exceeding one missing dose will not be counted for the analysis of the primary endpoint.

Participants may discontinue study intervention or be discontinued from the study at the discretion of the investigator should any untoward effect occur. In addition, a participant may be discontinued from study intervention by the investigator or the Sponsor if study intervention is inappropriate, the study plan is violated, or for administrative and/or other safety reasons. If study intervention is permanently discontinued, the participant should

29 NOV 2023 Page: 24 of 44

remain in the study to be evaluated at Visit 2 (Day 14). Discontinuation of study intervention does not represent withdrawal from the study.

A participant must be discontinued from study intervention, but continue to be monitored in the study for any of the following reasons:

- The participant experiences symptomatic hypotension of moderate to severe intensity (Section 10.3.3) during the treatment period.
- The participant or participant's legally acceptable representative requests to discontinue study intervention.
- The participant has a medical condition or personal circumstance, which in the opinion of the investigator and/or Sponsor, placed the participant at unnecessary risk from continued administration of study intervention.
- The participant has a confirmed positive serum pregnancy test.

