7.2 Participant Discontinuation/Withdrawal from the Study

- A participant may withdraw from the study at any time at the participant's own request, for any reason (or without providing any reason).
- A participant may be withdrawn at any time at the discretion of the investigator for safety, behavioral, or compliance reasons.
- At the time of discontinuing from the study, if possible, an unscheduled visit should be conducted, as shown in the SoA. See SoA for the data to be collected at the time of study discontinuation and follow-up and for any further evaluations that need to be completed.
- The participant will be permanently discontinued from the study intervention and the study at that time.
- If the participant withdraws consent for disclosure of future information, the sponsor may retain and continue to use any data collected before such a withdrawal of consent.

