8.4.1 Time Period and Frequency for Collecting AE and SAE Information

(S)AEs will be collected from the start of study intervention until the end-of-study visit (Visit 2) at the timepoints specified in the SoA (Section 1.3). (S)AEs which are related to protocol-required study procedures (e.g., (S)AE related to invasive study procedures or adjustment of therapy to comply with inclusion or exclusion criteria of the study) will be recorded as (S)AEs from the signing of the ICF.

Any medical occurrences/conditions that begin in the period between signing ICF and the start of study intervention, and which are not related to a protocol-required study procedure, will be recorded as medical history/current medical conditions, not as AEs.

All SAEs will be recorded and reported to the sponsor or designee immediately and under no circumstance should this exceed 24 hours of learning of the event, as indicated in Section 10.3. The investigator will submit any updated SAE data to the sponsor within 24 hours of it being available.

Investigators are not obligated to actively seek information on AEs or SAEs after conclusion of the study participation. However, if the investigator learns of any SAE, including a death, at any time after a participant has been discharged from the study, and the investigator

29 NOV 2023 Page: 28 of 44

considers the event to be reasonably related to vericiguat, the investigator must promptly notify the sponsor.

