8.4.5 Pregnancy

- Details of all pregnancies in female participants will be collected after the start of study intervention. The time period for reporting pregnancies should align with the time period for post-intervention contraception determined in Section 5.1.
- If a pregnancy is reported, the investigator will record pregnancy information on the appropriate form and submit it to the sponsor within 24 hours of learning of the female participant pregnancy.
- While pregnancy itself is not considered to be an AE or SAE, any pregnancy complication or elective termination of a pregnancy for medical reasons will be reported as an AE or SAE.
- Abnormal pregnancy outcomes (e.g., spontaneous abortion, fetal death, stillbirth, congenital anomalies, ectopic pregnancy) are considered SAEs, and will be reported as such.

29 NOV 2023 Page: 29 of 44

- The participant will be followed to determine the outcome of the pregnancy. The investigator will collect follow-up information on the participant and the neonate and the information will be forwarded to the sponsor.
- Any post-study pregnancy-related SAE considered reasonably related to the study intervention by the investigator will be reported to the sponsor as described in Section 8.4.4. While the investigator is not obligated to actively seek this information in former study participants, he or she may learn of an SAE through spontaneous reporting.
- Any female participant who becomes pregnant while participating in the study will discontinue study intervention or be withdrawn from the study.

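### No AE contact is planned up to Day 14 for dosed participants whom the investigator withdraws, so late related AEs can be missed in Secondary 1 (minor, cheap to close)

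*Protocol*

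**What the plan says.** **Retention.** Under Protocol 7.1, permanently stopping drug is not withdrawal, and the participant should still be evaluated at Visit 2. For four listed reasons, among them moderate to severe symptomatic hypotension and a confirmed positive serum pregnancy test, the rule is mandatory: "A participant must be discontinued from study intervention, but continue to be monitored in the study for any of the following reasons".

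**Exits.**
- Protocol 7.1, general sentence: "Participants may discontinue study intervention or be discontinued from the study at the discretion of the investigator should any untoward effect occur".
- Protocol 8.4.5: "Any female participant who becomes pregnant while participating in the study will discontinue study intervention or be withdrawn from the study".
- Protocol 7.2: "A participant may be withdrawn at any time at the discretion of the investigator for safety, behavioral, or compliance reasons".

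**After an exit.** Protocol 7.2 says "The participant will be permanently discontinued from the study intervention and the study at that time". It asks for a last visit only where feasible: "At the time of discontinuing from the study, if possible, an unscheduled visit should be conducted, as shown in the SoA". It then adds "See SoA for the data to be collected at the time of study discontinuation and follow-up". The Schedule of Activities has columns for Screening, V1, V2 and unscheduled visits only. Protocol 8.4.1 adds: "Investigators are not obligated to actively seek information on AEs or SAEs after conclusion of the study participation".

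**Analysis.** SAP Table 4-2 counts a participant as a Secondary 1 success if no related AE occurred between Visit 1 and Visit 2, with everyone in the SAF in the denominator. Missing data are not imputed (Protocol 9.3.2.2, SAP 4.1). SAP 4.1 lists unscheduled measurements but keeps them out of summary statistics and frequency tables. SAP 4.5.3.2 plans a summary of post-baseline hypotension criteria.

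**The concern.** AE collection is meant to run from first dose to Visit 2 (Protocol 8.4.1). Someone removed on, say, Day 4 may never have a Visit 2, and nothing in the protocol creates a substitute contact. In a proportion defined by the absence of a recorded event, an event that nobody asked about reads as tolerance. The study has a single arm, so there is no control group in which the same loss would occur. Its stated purpose is to support a change to the posology section of the label (Protocol 4.2). A loss that runs in one direction is worth closing even when it is small.

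A related gap concerns blood pressure. For someone removed early, the exit-visit reading may be the only planned reading after dosing, and the SAP's rule on unscheduled data leaves it out of the hypotension summary.

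**Working it through.** The plan states no figure on this point, so there is none to reproduce. The check is a comparison of the text followed by an illustration of size.

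**Step 1: which exits remain open?**
- *Moderate to severe symptomatic hypotension.* The general sentence in 7.1 is permissive, while the rule for this event is specific and mandatory. Read normally, the specific rule governs and the participant stays.
- *Other untoward effects.* The general sentence permits removal, against the aim stated in the same section.
- *Pregnancy.* 7.1 requires continued monitoring, while 8.4.5 offers withdrawal as an alternative. This is a plain mismatch, but it will be rare: a negative test is required within 24 hours before the first dose, and treatment lasts about two weeks.
- *Investigator withdrawal under 7.2.* This is open at any time. It is the main route, and it would survive edits to the other two passages.

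**Step 2: what is collected after an exit?**
- If the exit visit takes place, the Schedule of Activities makes AE review and vital signs mandatory.
- SAEs and AESIs already reported are followed to resolution or stabilisation (8.4.3). Symptomatic hypotension is an AESI (8.4.6).
- New events after the exit are not sought. Only an SAE that the investigator happens to learn of and considers related must be reported (8.4.1).

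**Step 3: which endpoints can move?**
- *Primary:* withdrawal under 7.2 ends treatment permanently, so the participant fails (Protocol 9.3.2.1). No change.
- *Secondary 1:* success is retained if no related AE has been recorded. A missed related AE can only raise the proportion.
- *Subgroups:* the ratios planned by subgroup are those of SAP Table 4-1. Secondary 1 is in Table 4-2, so no subgroup version of it is affected.

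**Step 4: size.** N is about 100 (Protocol 9.5, SAP 5), so one participant is 1/100 = 1 percentage point. Two inputs are assumptions, because the documents give neither:
- *r*, the removal rate: 0.5% to 2%.
- *p*, the chance that a removed participant with no earlier related AE has a first one by Day 14: 5% to 20%.

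Expected shift in points = 100 × *r* × *p*. Chance of at least one missed case = 1 − (1 − *r* × *p*)^100.

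| *r* | *p* | Expected shift (points) | Chance of at least one missed case |
|---|---|---|---|
| 0.5% | 5% | 0.025 | 2.5% |
| 1% | 5% | 0.05 | 4.9% |
| 1% | 20% | 0.2 | 18.1% |
| 2% | 20% | 0.4 | 33.0% |

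An expected shift of 1 point would need 1/0.20 = 5 removals per 100 at *p* = 20%, or 1/0.05 = 20 removals at *p* = 5%.

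**Step 5: blood pressure.** Protocol 7.2 makes the exit visit an unscheduled one, so SAP 4.1 excludes its readings from the tables. A participant who stops drug but stays has a scheduled Visit 2 reading. One who is removed does not. A symptom-triggered recheck after the first dose at Visit 1 may still supply a post-baseline value for some.

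**The case against.** The strongest reply is that the harm needs an unlikely chain. The participant must be removed despite the retention rule, have no related AE recorded by then, and have a first related AE afterwards while off drug but before Day 14. That AE must then go unreported. Someone removed for an untoward effect will normally have that effect recorded. If it is judged related, or its relationship is missing (SAP 4.5.2), that person already fails Secondary 1. Early exits will also be visible in the disposition table (SAP 6.1.1), and the study is descriptive with no success threshold. All of this stands, and it is why the point is minor. It leaves open removals for events judged unrelated and for behavioural or compliance reasons.

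Two stronger readings are tempting, and the documents do not support either.
- A reader might infer that sites are free to remove participants who have the very event the study measures. For moderate to severe symptomatic hypotension, the mandatory monitoring rule in 7.1 answers this.
- A reader might infer that AEs are discarded, because the treatment-emergent window ends at study completion, which Protocol 4.4 ties to Visit 2. SAP 4.5.2 states that the study defines no post-treatment AEs. Every AE recorded from first dose on therefore counts, and the gap is in collection alone.

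It is also fair to say that the blood-pressure exclusion applies to all unscheduled readings and does not stem from the removal wording. Its effect nevertheless falls on people removed early, who have no Visit 2 reading to replace the one left out.

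**Conclusion.** The point holds as a minor improvement. A dosed participant can leave before Day 14 with no assured exit visit and no later AE contact, and can still count as tolerant in Secondary 1. The direction is certain. The size cannot be derived from the documents. On the assumed ranges it is 0.025 to 0.4 points on one descriptive secondary proportion.

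Two larger claims should not be drawn from this.
- The primary endpoint is not biased, because removal is already a failure.
- A shift of about 4 points or more is not supported. That figure comes from the 3.9% (100% − 96.1%) of vericiguat participants in VICTORIA who did not stay on treatment uninterrupted to day 14 (Protocol 2.2). It mixes interruption with stopping, and it reaches 4 points only if every such participant were withdrawn from the study and every one had an unrecorded related AE.

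**What to change.** 1. **Protocol 7.2 (the change that matters).** Keep the investigator's discretion and add: *Every dosed participant whom the investigator withdraws and who has not withdrawn consent will have an AE review at Day 14 (+4), in person where possible and otherwise by telephone.* Add a matching exception to the 7.2 sentence that ends participation at withdrawal, and to the 8.4.1 sentence on not seeking AEs afterwards.
2. **Protocol 7.1 and 8.4.5.** Delete the alternative of leaving the study from the general untoward-effect sentence and from the pregnancy sentence, so that both agree with the continued-monitoring rule. On its own this does little, because 7.2 stays open.
3. **SAP 4.1 and 4.5.3.2.** Include post-dose blood pressure from exit (unscheduled) visits in the post-baseline hypotension summary.

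The treatment-emergent window in SAP 4.5.2 needs no change.

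**Cost.** An occasional extra visit or call, a small SAP edit, and a short protocol amendment. The amendment needs IRB/IEC approval before implementation (Protocol 10.1.1), which is a real burden for a study in which each participant takes part for about four weeks. Treatment-stopping rules do not change.
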